3.5. Selection of study population

3.5.1. Inclusion criteria

Baseline Phase One:

All infants discharged from Rwinkwavu hospital neonatal unit and born at less than 37 weeks and infants born less than 2 kilograms during the designated study period.

Post-PDC Phase Two:

All children under five years of age enrolled in PDC in Rwinkwavu District Hospital catchment area PDC clinics, will be included in Aim 3 and Aim 4b. Aim 4a will include only preterm and/or LBW (<2000g) infants for comparison with the baseline population of similar infants.

Expanding-PDC Phase Three:

All children under five years of age and their caregivers referred to or enrolled in PDC in Rwinkwavu and Kirehe District Hospital catchment areas. In addition, newborns and their caregivers from Rwinkwavu and Kirehe District Hospital catchment areas will be included as the primary referral patient population to PDC. PDC providers will also be included in some components of the evaluation.

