3.5.2. Exclusion and Stop Criteria

Pre-PDC Phase One:

1. Any infant whose family is unwilling to consent to study or decides to stop the home visit at any time.
2. Congenital heart disease per neonatal register
3. Genetic dysmorphology per neonatal register
4. Birth asphyxia per neonatal register

Post-PDC Phase Two:

1. For Aim 4a, exclusion criteria will match the Baseline Phase One exclusion criteria listed above.

Expanding-PDC Phase Three:

1. Children who do not meet inclusion criteria will be excluded.

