3.6.2. Outcomes, exposures, and confounders to be measured

Pre-PDC Phase One:

Aim 1: Describe the baseline outcomes of a selected sample of infants discharged from a rural hospital neonatal unit.

1. *Primary Outcome:*

The primary outcome is the proportion of study participants alive with developmental delay.

Developmental delay is defined as one domain that is scored as an area of concern or presence of delay using the Ages and Stages Questionnaire (ASQ-3).

2. *Secondary Outcomes:*

1. Proportion of study subjects deceased
2. Proportion of study subjects with malnutrition
3. Proportion of study subjects with medical co-morbidities, further broken down into the four categories: hydrocephalus, anemia, feeding difficulty, and respiratory disease.
4. Proportion of the study subjects with developmental delay and malnutrition
5. Proportion of study subjects with developmental delay and medical comorbidities

Aim 2: Identify specific patient-level predictors of developmental delay. Main exposures of developmental delay include prematurity, low birth weight and malnutrition. Potential

confounders include but not limited to sector of residence, sex, ubudehe category (measure of economic status), household size, and education level.

Post-PDC Phase Two:

Aim 3: Describe the PDC. This aim is to describe the pediatric development clinic (PDC) after 24 months of implementation in terms of the following main outcomes: services provided, referral system, patient population served and clinical, nutritional, and developmental status after support and follow-up in the clinic.

Other Variables to be measured include (See Appendix F for data source forms)

Characteristics of Clinic Patients

Proportion of study participants per age category and per medical condition.

Broken down by:

- Proportion of infants
- Proportion of children from one year to five years
- Proportion of children born premature
- Proportion of ELBW/ VLBW
- Proportion of infants born at term with HIE or cerebral infection

Proportion of children with developmental delays, trisomy 21, hydrocephalus, cleft lip/palate, and developmental delay

- Proportion of children deceased
- Proportion of children lost to follow-up
- Proportion of children with malnutrition per age category or per medical condition

Clinic activities will be described

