Aim 4a: Compare developmental, medical, and nutritional outcomes of children who were enrolled in the PDC to medically vulnerable children who did not receive PDC support (from Baseline Phase One)

Analysis Plan:

We will use bivariate analyses to compare the outcomes of infants who received PDC services with those who did not receive these services (the baseline data from Phase One). Developmental delay will be scored as a binary outcome looking at the proportion of children who failed one or more ASQ-3 domain at baseline to the proportion of children enrolled in PDC who failed one or more ASQ-3 domain. We will use a chi square test or fishers exact test look for significant differences in the number of children with developmental delay between children who received PDC services and those who did not. Chi squared or fishers exact tests will also be used to assess for differences in nutritional outcomes (normal, moderate, and severe malnutrition indicators) and medical outcomes among the two groups.

If we have sufficient power, we will conduct logistic regression analyses to look at predictors of developmental delay in the sample. Using backwards selection, all variables associated with developmental delay at $p < 0.10$ in bivariate will be included in the full model. We will report Odds Ratio, p-value, and 95% confidence intervals for multivariate analyses.

Aim 4b: Compare developmental, medical, and nutritional outcomes of children who were enrolled in the PDC to a sample of Rwandan children from ten rural sectors across the country.

Analysis Plan:

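### Aim 4a's entry rule leaves no term child of 2000 g or more, so a bivariate p<0.10 screen can understate prematurity and leave birth weight confounded in the predictor model

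*Combined protocol and SAP*

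**What the plan says.** Section 3.5.1 (Inclusion criteria, Phase Two) states: "Aim 4a will include only preterm and/or LBW (<2000g) infants for comparison with the baseline population of similar infants". The Phase One rule in the same section covers infants "born at less than 37 weeks and infants born less than 2 kilograms during the designated study period". Section 3.5.2 carries the Phase One exclusions over to Aim 4a, and none of them adds back a heavier term child.

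Section 3.6.4 (Aim 4a) makes the predictor model conditional on sufficient power; if that is met, "we will conduct logistic regression analyses to look at predictors of developmental delay in the sample". Variables associated with delay at p<0.10 "in bivariate will be included in the full model", and selection is backwards. No variable is forced in, and no candidate list is given for Aim 4a.

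The candidates have to be read from Aim 2. Section 3.6.2 says there: "Main exposures of developmental delay include prematurity, low birth weight and malnutrition". Section 3.6.4 (Aim 2) hypothesises that birth weight (four bands, the top one 2 kg or more) and gestational age (under 32, 32–36, 37 weeks or more) are both associated with delay. Section 2 says Aim 2 itself will not be completed.

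**The concern.** A preterm child can enter Aim 4a at any weight, but a term child can enter only below 2000 g. The sample therefore holds three kinds of child, and the fourth cell (term, 2000 g or more) is empty by design. Within such a sample the two entry criteria are negatively related. A bivariate test of prematurity compares preterm children of mixed weight with term children who all carry the other risk factor.

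A screen built on that test can reject prematurity, and the low-weight estimate that remains is then itself confounded. The reported list of predictors would partly reflect who was let into the sample. The limitations in section 4 mention misclassification, missing values and cross-sectional design, but not this selection.

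**Working it through.** **Inputs from the documents.** The entry rule (3.5.1), the p<0.10 bivariate screen with backwards selection (3.6.4, Aim 4a), and the weight and gestation bands (3.6.4, Aim 2). The bands for 37 weeks or more and 2 kg or more show that the plan expects both term children and heavier preterm children. That supports reading the loosely worded Phase One rule as either criterion rather than both.

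**Inputs assumed.** The plan gives no Aim 4a sample size, delay rate or odds ratio, so there is no stated figure to reproduce. I take baseline odds o = e⁻¹ = 0.368 (risk 27%), a preterm odds ratio P, a low-weight odds ratio L, and the mixes shown below.

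**Formula.** Cell odds are:
- A (preterm, <2000 g): o·P·L
- B (preterm, ≥2000 g): o·P
- C (term, <2000 g): o·L

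Risk = odds/(1+odds). Crude preterm OR = odds of the weighted mean risk in A and B, divided by the odds in C.

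**Worked case: mix A/B/C = 50/35/15, P = 2, L = 2.** Risks are A 0.595, B 0.424, C 0.424. Mean preterm risk = (50×0.5954 + 35×0.4239)/85 = 0.525, odds 1.104. Crude OR = 1.104/0.736 = 1.50, against a true 2.

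**Same mix, L = 3.** Risks are A 0.688, B 0.424, C 0.525. Mean preterm risk = (50×0.6882 + 35×0.4239)/85 = 0.579, odds 1.377. Crude OR = 1.377/1.104 = 1.25.

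| True P, L | Crude preterm OR, 75/10/15 | 50/35/15 | 40/50/10 |
|---|---|---|---|
| 2, 2 | 1.84 | 1.50 | 1.36 |
| 2, 3 | 1.74 | 1.25 | 1.07 |
| 1.5, 3 | 1.31 | 0.955 | 0.82 |
| 2, 4 | 1.65 | 1.08 | 0.89 |

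With L = 1, or with no child in cell B, the crude OR equals the true P and there is no bias.

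**What happens to the factor that stays.** At 50/35/15 the crude low-weight OR is 1.70 for (2, 2), 2.53 for (2, 3) and 2.73 for (1.5, 3). Low weight is also attenuated, but less.

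**Chance of passing the screen.** Simulation at 50/35/15 with an assumed 240 children:

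| True P, L | Binary preterm screen, harmful direction, p<0.10 | Both factors in one model, harmful direction, p<0.10 |
|---|---|---|
| 2, 2 | about 30% | 56% |
| 2, 3 | about 15% | 55% |
| 1.5, 3 | about 3–4% | 29% |

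With gestational age in the plan's three bands, and assuming that 20% of the sample is under 32 weeks and below 2000 g, the screen passes in about 40–50% of samples when those children carry no extra risk. It passes in about 77–96% when their extra odds ratio is 1.5 to 2. It passes largely through the under-32-week band, and the contrast with term children stays biased.

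**After entering both factors together.** In simulations with 20% term children, half of the preterm children at 2000 g or more, and a baseline delay risk of 25%, the median adjusted preterm OR is 1.98–2.05 for a true 2. The crude values are 1.38–1.42 (L = 2) and 1.13–1.14 (L = 3). This recovery is partly by construction, because the fitted model is the one that generated the data.

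**The case against.** Several objections stand in part.

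- **The candidates are inferred.** Aim 4a names no predictors; prematurity and birth weight come from an aim that was dropped. That is so, but a model of delay in children selected on these two criteria would hardly leave them out.
- **The specified coding is three bands, not preterm yes/no.** This stands. The low pass rates for a binary screen do not describe a three-band variable, which is dropped less often.
- **Part of the loss is low power.** This stands. Even the joint model reaches p<0.10 in only 29–56% of the simulated samples. With no weight effect and a preterm OR of 2, the binary screen passes in about 54%.
- **The model is secondary and conditional.** This stands. It runs only with sufficient power, and the comparison of clinic children with baseline children is a separate test.
- **Section 4 already disclaims causality.** It does, but it says nothing about selection on the exposures.

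A reader might infer that the screen will make prematurity look harmless or protective. The documents do not support that. Reversal needs many heavier preterm children and a weight effect much stronger than the prematurity effect, and the plan gives neither rate. A reader might also infer that crude odds ratios for the two factors should not be reported at all. That goes too far: a crude odds ratio correctly describes this sample, provided it is labelled.

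**Conclusion.** The point holds in conditional form. The empty cell follows from the entry rule alone, with term meaning term as recorded. The downward bias in the crude preterm contrast needs two conditions: low weight raises the risk of delay, and some preterm children weigh 2000 g or more. The plan's hypothesis and bands presume both.

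The size cannot be fixed from the documents. For a true preterm odds ratio of 2 and a low-weight odds ratio of 2 to 3, it runs from modest (crude 1.84 to 1.74 with 10% heavier preterm children) to substantial (1.50 to 1.25 with 35%). The consequence is confined to the Aim 4a predictor model, where the screen can drop one factor and leave the other confounded.

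**What to change.** In section 3.6.4, Aim 4a, add that if the predictor model is run:

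1. Gestational age and birth weight are entered together, in the Aim 2 bands or as continuous variables, exempt from both the bivariate screen and backwards selection.
2. Any crude odds ratio for either factor is labelled as confounded by the entry rule.
3. The report states that the sample holds no term child of 2000 g or more, so the interaction of the two factors cannot be estimated.

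Both variables are already listed for analysis, so nothing new has to be collected. The cost is that a few model parameters are always spent on them: two if both are continuous, and up to five with three gestation bands and four weight bands (2 + 3), which matters if delays are few.

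The change does not cure everything. The adjusted preterm-versus-term contrast rests on children below 2000 g, and term children that small may differ in unmeasured causes of poor growth.

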3.6.4. Analysis Plan

Pre-PDC Phase One:

Aim 1: Describe the baseline outcomes of a selected sample of infants discharged from a rural hospital neonatal unit.

Analysis Plan:

The primary analysis will be a univariate analysis describing the proportion of children discharged from the neonatal unit with developmental delay at two years of age. This is the primary outcome of the study and will provide vital data regarding neonatal outcomes at two years after discharge from neonatal unit. Proportions will be calculated for categorical variables and means with standard deviations will be calculated for continuous variables.

Categorical variables include: sex, sector, alive/dead, malnutrition (yes/no), malnutrition category (low, moderate, severe), medical comorbidities (anemia, respiratory disease,

possible hydrocephalus, and feeding difficulty), ubudehe category (measure of economic status), and education level of the caregiver.

Continuous variables are birth weight, gestational age, age at the time of data collection, and household size.

Aim 2: Identify specific patient-level predictors of developmental delay

Analysis Plan:

We hypothesize that birth weight (< 1kg, 1-1.5kg, 1.5-<2kg, \geq 2 kg), gestational age (<32 weeks, 32-36 weeks, \geq 37 weeks), and malnutrition (yes/no) will be significantly associated with developmental delay in bivariate and multivariable analyses.

Chi square test will be performed to test for associations between these categorical variables and the primary outcome (developmental delay). A multivariable logistic regression model will be created to identify predictors of developmental delay controlling for potential covariates using the same list of descriptive variables. However, this analysis will only be performed if there are a sufficient number of children with the primary outcome to have sufficient power to detect predictors.

Post-PDC Phase Two:

Aim 3: Describe the PDC and patients enrolled in the PDC

Analysis Plan:

Demographic characteristics, services provided to patients, and clinical, nutritional and developmental outcomes will be described using descriptive statistics. For continuous variables, mean and standard deviations will be reported unless the distribution is not normal and then medians and inter-quartile range will be reported. Frequencies and percentages will be reported for categorical variables.

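### The conditional Aim 4a predictor model reports ordinary 95% intervals after two rounds of outcome-driven selection, so average coverage over the reported predictors falls below 95%, mainly through null and weak predictors

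*Combined protocol and SAP*

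**What the plan says.** Section 3.6.4 gives Aim 4a two analyses. The main one is unadjusted: "We will use bivariate analyses to compare the outcomes of infants who received PDC services with those who did not receive these services", by chi-square or Fisher's exact test, with delay scored as a binary outcome.

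The second is conditional: "If we have sufficient power, we will conduct logistic regression analyses to look at predictors of developmental delay in the sample". No criterion for sufficient power is given. The model is built in two steps, both using the outcome. The screen is that "all variables associated with developmental delay at $p < 0.10$ in bivariate will be included in the full model", and the sentence opens with "Using backwards selection". No removal level is stated and no term is forced in, not even PDC group. The output is fixed: "We will report Odds Ratio, p-value, and 95% confidence intervals for multivariate analyses".

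Aim 4a has no candidate list. The nearest is in the Aim 2 plan, "controlling for potential covariates using the same list of descriptive variables", which points back to the Phase One descriptive variables; section 2 says Aim 2 will not be completed. Section 3.6.2 also names about seven caregiver and household measures under Aim 4 without saying whether they are candidates. The Phase Two limitations in section 4 disclaim causality but do not mention selection.

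**The concern.** An ordinary 95% interval assumes that the model was fixed before the outcome was seen. Here a variable reaches the table because its estimated association with delay was large enough in these same data. Among variables chosen that way, estimates tend to be too far from the null and intervals miss the truth more often than 5% of the time. Selected variables with no real association fare worst.

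This is the only place in the Aim 4 analysis plan where confidence intervals are promised, and the only multivariable analysis in that aim. A reader would take the table at face value as showing which children are at higher risk of delay. Because PDC group is not forced in, any adjusted PDC odds ratio would itself appear only if it survived selection.

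**Working it through.** **Inputs.** From section 3.6.4: binary outcome, p<0.10 screen, backwards selection, ordinary 95% intervals. Assumed, because the documents do not state them: total n of 120, 240 or 400 (the only count in the documents is 120 participant incentives in the Phase One budget); 40% with delay, with 20% as a sensitivity value; 10 to 20 candidates; removal at 0.05 or 0.10. The plan has no coverage or power figure to reproduce.

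**Step 1. A retained null predictor.** Suppose the true odds ratio is 1 and removal is at 0.05. The variable stays only if p<0.05, which means its Wald 95% interval excludes 1. Coverage given retention is therefore 0% by construction. With removal at 0.10, simulation puts it at about 37–46%.

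**Step 2. Average coverage, few weak effects.** Simulation (1,000 samples per setting): independent candidates, three real with OR 1.4 per SD, the rest null.

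| n | candidates | removal | coverage over reported predictors | at least one null with p<0.05 | mean selected real OR |
|---|---|---|---|---|---|
| 240 | 20 | 0.05 | 68.5% | 56% | 1.53 |
| 240 | 12 | 0.05 | 79% | 38% | 1.52 |
| 120 | 20 | 0.05 | 55% | 55% | 1.77 |
| 400 | 20 | 0.05 | 75% | 55% | 1.44 |
| 240 | 20 | 0.10 | 75% | 55% | 1.50 |

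Other runs of these settings differ by a few points; the lowest coverage seen at n=120 was 51%. Across runs the false-positive column spans about 36–60%. The full list fitted once covers 93–95%, averaged over all its terms.

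**Step 3. Average coverage, stronger effects.** Simulation (2,000 samples per setting): 15 binary candidates, one with OR 3, two with OR 2, two with OR 1.5, ten null. With removal at 0.05, coverage is 73% (n=120), 83% (n=240) and 87% (n=400). With removal at 0.10 it is 80%, 87% and 90%. At 20% delay, n=240 and removal at 0.05, it is 80%.

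**Step 4. Where the loss falls.** Take n=240, removal at 0.05, from Step 3.

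| true OR | number × chance reported | coverage if reported | expected covered |
|---|---|---|---|
| 1 | 10 × 0.036 = 0.360 | 0 | 0 |
| 1.5 | 2 × 0.316 = 0.632 | 0.881 | 0.557 |
| 2 | 2 × 0.694 = 1.388 | 0.942 | 1.307 |
| 3 | 1 × 0.974 = 0.974 | 0.962 | 0.937 |
| total | 3.354 | | 2.801 |

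2.801/3.354 = 0.835, which matches the simulated 83%. Leaving out the nulls gives 2.801/2.994 = 0.936. Almost all of the shortfall here comes from retained nulls. Over all Step 3 settings, coverage is 79–95% for OR 1.5, 90–97% for OR 2 and 93–96% for OR 3.

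**Step 5. Chance findings.** For m independent nulls tested once at 0.05, P(at least one) = 1 − 0.95^m.
- m = 17 (20 candidates, three real): 1 − 0.95^17 = 58.2%.
- m = 9 (12 candidates): 1 − 0.95^9 = 37.0%.
- m = 4 (seven terms, three real): 1 − 0.95^4 = 18.5%; simulated, about 18–21%.

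The first two are close to the selected-model rates in Step 2. The unselected 20-variable model gives 62–70% in simulation. The rate therefore follows the number of null candidates, and selection does not raise it.

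**The case against.** The strongest reply is that selection is blamed for what multiplicity does. On false positives this is right: fitting the same long list once gives as many or slightly more. The coverage contrast is also not like for like, because 93–95% averages over all terms of the full model. Among full-model terms with p<0.05, coverage was 62% at n=240 and 44% at n=120, and real odds ratios picked that way averaged 1.59, against 1.54 after selection. What still stands is that selection hides the discarded terms, so the reader sees only the chosen ones, each with an unqualified 95% label. A pre-specified model reported in full does not have that problem.

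The model is also secondary and gated on power. A reader might take the dropping of Aim 2 for small numbers as proof that this model is doomed. The documents do not support that: Aim 2 used Phase One children alone, Aim 4a adds PDC children, and the Aim 2 decision shows that such a gate has been applied. The smallest setting, n=120, may be one the gate would exclude.

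The candidate count is uncertain too. The Phase One list includes vital status, which cannot predict delay among living children, and counts malnutrition twice. Section 3.6.4 does not make the household measures candidates. This is why 12 to 20 is shown as a range.

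**Conclusion.** The point holds for the conditional Aim 4a predictor model. Its reported 95% intervals do not have 95% coverage averaged over the predictors in the table. Under the stated assumptions, average coverage is about 51–79% with weak effects and removal at 0.05, about 75% with removal at 0.10, and about 73–90% with stronger effects. The direction was the same in every setting tried; the size cannot be fixed from the documents.

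Three stronger readings are not supported. First, a reader might infer that every interval is far too short on coverage, but strong predictors stay near 95%. Second, a reader might infer that the Aim 4a comparison of PDC with baseline is compromised, but it is a separate unadjusted test that this selection does not touch. Third, a reader might infer that these predictors will decide whom the clinic serves, but section 3.5.5 sets eligibility by listed conditions and no section gives the model that use.

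**What to change.** In section 3.6.4, Aim 4a, replace the p<0.10 screen and backwards selection with one short logistic model named in advance, fitted once, with all terms reported. Force in PDC group. Take the rest from variables already named in section 3.6.2 and the Phase One parts of 3.6.4: birth weight and/or gestational age, malnutrition, sex, age at assessment, ubudehe category, household size, caregiver education and sector in grouped form. If events are few for that list, use Firth or ridge penalisation rather than selection.

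Two cautions apply. The list has nine or ten items, so the gain in false positives depends on how many are null: with six nulls, 1 − 0.95^6 = 26.5%, still below the 36–60% above. And because the clinic gives nutritional support and undernutrition is itself an Aim 4 outcome, the PDC odds ratio from a model containing malnutrition should not be read as the total PDC effect.

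If selection is kept, state the candidate list and removal level, label the model exploratory, and take intervals from a bootstrap that repeats both selection steps.

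The cost is plan wording only, with no new data. The downside is wider intervals and some listed variables showing no association.
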